The research coordinator will obtain the providers' written informed consent for the study participation; a fully signed copy will be provided to the provider and another copy will be kept on file in a locked cabinet in [name] office at MetroHealth.

Following recruitment and informed consent procedures, OB providers will be randomized by practice into one of two study arms: (1) the intervention arm utilizing NEST or (2) the control arm utilizing standard practice patterns for education and counseling (usual care). Randomization by practice will prevent contamination between study arms, as a patient may see more than one provider within a practice over the course of her pregnancy. A cluster will be an outpatient clinic and contain the providers who practice at that location. The intervention will be delivered to the cluster as a whole. Thus, all participating providers within a cluster will be randomized to the same arm. Practices within the healthcare system will be stratified by both practice and patient-population characteristics. A binary random number generator will be used to assign NEST or control status at the practice level. The assignment will be checked to ensure a balance with respect to the number of clusters and providers in each of the study arms. Imbalances will be corrected manually, and the resultant groupings will be checked to ensure that randomization has been preserved. Participating providers in practices randomized to the intervention arm will receive a training session to orient them to NEST prior to data collection activities. Because NEST is targeted to affect the patient-provider interaction, study participants will not be blinded to which group they have been allocated.

All participating providers at Cleveland Clinic and MetroHealth will be asked to review the most current clinical practice guidelines as developed by the American College of Obstetricians and Gynecologists (ACOG) and Society for Maternal Fetal Medicine (SMFM). These guidelines will be emailed to each provider once their first patient has expressed interest in participating.

We will return to previous methods of enrolling providers into the NEST study at both MH and CCF.

DATA COLLECTION INSTRUMENTS AND PROCEDURES

We will utilize the same data collection instruments at both the Cleveland Clinic and at MetroHealth.

I. Pregnant participants

Data collection instruments and intervention:

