1) QBASE: Once informed consent has been obtained, all participants will complete the QBASE. This will be administered on a CCF-compliant tablet and using REDCap survey. The research team member does come with a paper copy of the QBASE as a backup for any technical difficulties. If the paper survey is used, it would be manual entered by the research team into REDCap.

2) NEST Intervention: Participants scheduled to see an OB provider randomized to the NEST (randomization occurs at the level of the OB provider) will be asked to complete the NEST. This will be administered on a CCF-compliant tablet and using REDCap survey. After completion, patient participant will be given two printed copies of the NEST, one for the patient and one for their provider, to review during their office visit. The participating provider will be given a copy of the NEST to help tailor the conversation to the patient's needs. Patients who are scheduled to see a provider at a practice randomized to the control arm will receive standard care.

As recent guidelines have changes, we will again be enrolling patients from designated intervention branches for the CCF and MetroHealth sites.

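### Imbalances are corrected by hand after the random draw, with no rule, random element or independent allocator, which permits non-random reassignment of practices

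*Combined protocol and SAP*

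**What the plan says.** The allocation procedure is in the combined protocol and SAP, under Participants and Recruitment Procedures, section III (OB providers), after the MetroHealth provider recruitment steps. In order, it states:

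- Timing: "Following recruitment and informed consent procedures, OB providers will be randomized by practice into one of two study arms".
- Unit: "A cluster will be an outpatient clinic and contain the providers who practice at that location".
- Strata: "Practices within the healthcare system will be stratified by both practice and patient-population characteristics".
- Draw: "A binary random number generator will be used to assign NEST or control status at the practice level".
- Inspection: "The assignment will be checked to ensure a balance with respect to the number of clusters and providers in each of the study arms".
- Correction: "Imbalances will be corrected manually, and the resultant groupings will be checked to ensure that randomization has been preserved".
- Blinding: "study participants will not be blinded to which group they have been allocated".

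The strata are not listed, and the text does not say how the generator works within them. No blocks, fixed arm totals or balance tolerance are described. A statistician is mentioned in the Data Analysis section, for the analysis only.

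One further sentence, in the NEST Intervention item of the data collection procedures for pregnant participants, gives a different unit: "randomization occurs at the level of the OB provider". That is a separate inconsistency, but it must be reconciled with the practice-level text before any allocation rule can be written.

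**The concern.** Random allocation protects the comparison because chance alone decides which arm each cluster enters. If a practice can be moved after its result is seen, and nothing says how it is picked, chance need not decide that practice's arm.

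Several features of this trial make the step sensitive:

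- When the assignment is reviewed, the consenting providers and their clinics are already known. Providers complete a baseline survey at enrolment that covers their confidence with prenatal testing topics and shared decision-making, and the coordinator holds the responses. Nothing bars the person making the correction from knowing them.
- The primary outcome is shared decision-making observed in the visit, which depends directly on the provider. A clinic placed in an arm because its providers seem receptive would shift that outcome.
- Participants are not blinded, so sound allocation is one of the few protections against bias that remain.
- Whole clinics are allocated, so each move carries all of a clinic's providers and patients with it.

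At stake is whether the main comparison can be described as randomised.

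**Working it through.** The plan states no number of practices, tolerance or other figure for this step, so there is nothing to reproduce. The finding rests on steps 1 to 3. Steps 4 to 6 are illustrations under stated assumptions.

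**1. Sequence.** Consent, stratification, draw, inspection, manual correction, second check. The correction follows both the consent of providers and sight of the generated result.

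**2. What would make the correction random?** A preset trigger, a rule for which practice moves, a random choice among eligible practices (or a re-draw to a preset criterion), and someone independent of recruitment to carry it out. The documents give none of these.

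**3. What can the second check show?** Randomness is a property of the process. The same final grouping can arise from a random swap or from a deliberate one, so looking at the grouping cannot tell them apart. No test or criterion for the check is named.

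**4. How often would counts differ?** Assumptions: N practices, independent fair draws, no strata, exact equality as the goal. N = 8, 12 and 20 are assumed values.

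P(unequal counts) = 1 − C(N, N/2) / 2^N

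- N = 8: 1 − 70/256 = 0.727
- N = 12: 1 − 924/4,096 = 0.774
- N = 20: 1 − 184,756/1,048,576 = 0.824

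Over an assumed range of 6 to 24 practices the figure runs from 69% to 84%. A looser trigger lowers it: a difference of 4 or more clusters occurs in 29%, 39% and 50% of draws for N = 8, 12 and 20. Provider counts are a second trigger that is not included here.

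**5. How much latitude would a correction leave?** A difference of 2 is removed by moving any one practice from the larger arm, and a difference of 4 by moving any two.

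| N | Difference of 2: choices | Difference of 4: choices |
|---|---|---|
| 8 | 5 (from 5:3) | C(6,2) = 15 |
| 12 | 7 (from 7:5) | C(8,2) = 28 |
| 20 | 11 (from 11:9) | C(12,2) = 66 |

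The generator does not select among these choices, and neither does any written rule.

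**6. Do the strata help?** If each practice is drawn independently, balance within strata is not enforced. With s strata of m practices, P(at least one stratum unbalanced) = 1 − [C(m, m/2) / 2^m]^s. For 2 strata of 4 this is 1 − (6/16)² = 0.859. For 4 strata of 4 it is 1 − (6/16)⁴ = 0.980. The strata are undefined, so these layouts are assumptions too.

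**The case against.** The strongest reply is that the text is incomplete rather than wrong. Correcting by hand could mean repeating the draw, or picking at random the practice to switch, and the stated aim is to keep the allocation random. A re-draw to a preset balance criterion would be a recognised form of restricted randomisation. This stands as far as it goes: a reader might infer that staff chose which clinics received NEST, or that the trial's randomisation was broken, and the documents support neither. They name no one who makes the correction and report no move. But good intent is not a procedure, and the wording equally allows a discretionary swap.

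A reader might also infer that the correction undoes the stratification. The text does not say that the draw ignores the strata. What can be said is that the strata and their mechanics are undefined, and that an unrestricted draw does not enforce balance within them.

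The Data Analysis section plans a multivariable analysis that includes patient and provider characteristics. That may reduce bias from measured differences. It cannot remove selection on unmeasured ones.

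The probabilities in the working describe how often counts differ. They do not measure bias in the treatment effect, and they depend on an assumed number of practices and an assumed trigger.

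Finally, the document is a continuing renewal. Provider recruitment had started by 2019, and the NEST Intervention item refers to intervention branches as already designated, so some practices have probably been allocated. A new allocation scheme may reach few clusters. This limits the prospective part of the fix but leaves the need to document past allocations.

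**Conclusion.** The point holds as a defect in the written procedure. The plan directs manual correction after the result is seen and after providers have consented, and it supplies nothing to keep that correction random. The later check cannot fill the gap. This rests on the text alone and needs no assumption about the number of practices.

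The size can only be illustrated. If exact equality of cluster counts is the goal, with a fair unstratified draw, correction would be called for in 73%, 77% and 82% of cases for 8, 12 and 20 practices. A reader might take this to mean that practices in this trial were in fact moved, or that the treatment effect is biased by some amount. The documents show neither, and the possible bias cannot be quantified from them. Confidence is high that the rule is missing. There is no basis for a view on whether any selection took place.

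The matter should be settled before the analysis, because without a record of generated and final arms a reader cannot tell whether the main comparison is randomised.

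**What to change.** **Practices not yet allocated.** Replace the manual-correction sentence with a one-step computer allocation that has balance built in. Two options would serve:

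- permuted blocks within defined strata; or
- covariate-constrained randomisation on health system, number of providers and patient mix, with one scheme drawn at random from the acceptable set.

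Define the strata or constraints in advance, and have the statistician run the allocation independently of recruitment. This meets the investigators' legitimate wish for balance without a manual stage.

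**Practices already allocated.** Keep the description of what was done, as it is part of the trial's history. Record the generated and the final arm of each practice, state who made any correction and on what basis, and disclose every move in the report.

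**Analysis.** If any practice was moved and its generated arm can be recovered, add a sensitivity analysis by generated arm. State that it dilutes the effect, because a moved clinic actually received the other arm. For example, if one practice moved to turn 7:5 into 6:6, then with equally weighted practices and a constant effect the estimate by generated arm is 6/7, or about 86%, of the effect. An analysis that leaves out moved practices is secondary, because it loses precision and is itself a non-random selection.

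**Cost.** A short amendment, disclosure of any past moves, and the work of reconstructing the generated assignments, which may not have been kept. If they cannot be recovered, the report should say so.

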3) We would like to initiate a new approach to support successful recruitment: utilizing a paper version of the recruitment package, including our recruitment letters (previously IRB approved, and with a current stamp). This recruitment package would be sent to the eligible provider either through 1) Cleveland Clinic interoffice mail, 2) USPS, or, 3) Hand delivery to office manager or assistant

Since our initial recruitment efforts in 2019, the WHI has on-boarded a large number of new OB providers. We would like to reach those providers in addition to existing providers who did not respond to the initial recruitment emails and those who voiced initial interest the study but did not follow up to our recruitment efforts. In this process, we would NOT contact any providers who communicated that they did not want to be in the study or did not want to be contacted by the research team. We will only be reaching out to eligible providers who:

- Eligible providers who have never been contacted by the Research Coordinator regarding participation in this study (new staff since 2019).
- Providers who were previously sent recruitment information, expressed interest but never completed the informed consent process.
- Providers who were previously sent recruitment information but did not respond to that communication.

Once the provider responds to the initial e-mail with a signed copy of their informed consent for study participation, the research coordinator will send a copy with her signature back to for the provider to keep in their records and a copy will be kept on file in a locked cabinet in the NEST office at WHI.

MetroHealth:

The following recruitment procedures have been developed in conjunction with [name], co-investigator on the NIH application and former site PI at MetroHealth, and will be maintained by the new site PI, [name].

1) The research coordinator will send a recruitment email describing the nature of the study to each provider who meets inclusion criteria. The email will also include the consent form for the provider to review.

2) In addition, [name], the site PI, will be involved in recruitment of OB providers. [name] will send an IRB-approved follow up email to providers who do not respond within one week to the initial email sent by the research assistant.

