Study Intervention: We will also utilize the following questionnaire as the study intervention. The intervention (NEST) is also a questionnaire. NEST is a point of care shared decision-making tool. NEST is structured as a self-administered survey completed by the participant prior to the initial prenatal visit. Survey questions pertain to baseline knowledge of concepts associated with NIPT, fetal genetic risk and assessment, and decision-making preferences and priorities with respect to prenatal testing. NEST is divided into three sections. Section 1 contains a series of questions to ascertain patients' familiarity with: the different prenatal genetic screening and diagnostic tests; the conditions that can be detected using prenatal screening and testing, as well as terms used to describe these tests. Section 2 addresses informational and decision-making priorities to set the agenda of the conversation. This section addresses concepts associated with scientific and medical aspects that form the basis of decisions about NIPT and alternate prenatal tests. Section 3 contains open-ended questions so that the patient can provide additional information, as well as questions to further personalize the discussion. Those participants who are seeing a doctor or midwife randomized to the intervention arm may complete NEST online at the time of completing QBASE or on a secure iPad in the clinical area before the initial prenatal visit. A printed summary of the NEST data reporting the patient's needs and priorities will guide the provider to structure a patient-centered shared decision making process. The NEST report will be generated from the data entered into the NEST using REDCap survey. It will contain no other information but merely be a presentation of the pregnant patient-entered data. The research assistant will print the NEST Report and review it with the pregnant patient. The patient will be provided with a copy of the NEST Report to reference during the visit and to share with her partner based on her preferences. As part of the informed consent procedures, the pregnant woman will be made aware that she does not need to share this information with her partner as part of study procedures. A copy of the NEST Report will then be given to the provider to review prior to the clinical visit to tailor the content and focus of the discussion with the patient about her different screening and testing options.

Data collection procedures:

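### The NEST procedure gives the OB provider as the randomised unit, the randomisation text gives the practice, and the analysis section names no cluster that would settle it

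*Combined protocol and SAP*

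**What the plan says.** The combined protocol and SAP describes allocation in one place, the paragraph that follows provider recruitment under III. OB providers. There, "OB providers will be randomized by practice into one of two study arms". The cluster is defined: "A cluster will be an outpatient clinic and contain the providers who practice at that location". The mechanism is given: "A binary random number generator will be used to assign NEST or control status at the practice level". The consequence is spelled out: "all participating providers within a cluster will be randomized to the same arm". The stated reason is to prevent contamination, since a woman may see several providers in one practice during her pregnancy.

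The NEST Intervention item under Data collection procedures for pregnant participants tells staff which women are asked to complete NEST. Its parenthesis reads "randomization occurs at the level of the OB provider". The last sentence of that item describes control patients as those seeing a provider at a practice that was randomised to control.

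The Cleveland Clinic provider recruitment text, item 3, records that since 2019 "the WHI has on-boarded a large number of new OB providers" and sets out how they will be approached.

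The Data Analysis section compares measures by exposure and by visit composition, and lists provider characteristics among the candidate predictors. It contains no practice or provider random effect, no cluster-level analysis, and no statement of the unit on which standard errors are based.

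**The concern.** The unit of randomisation fixes both who gets the intervention and what counts as an independent observation. Here it is stated two ways in current text.

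Two things follow. First, the provider pool is still growing. Apart from the general same-arm rule, the plan does not say how a provider who joins an already assigned practice gets an arm, and the parenthesis points to a different answer from that rule. Second, an analyst who turns to the Data Analysis section finds no unit there. One who then relies on the parenthesis would treat providers as independent. If practices were randomised, outcomes shared within a practice would be left out of the error term, and confidence intervals and p-values for NEST against control would be too optimistic.

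**Working it through.** **The statements side by side**

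| Place | Unit stated or implied |
|---|---|
| III. OB providers, randomisation paragraph | Practice (method, cluster definition, same-arm rule, mechanism, rationale) |
| NEST Intervention item, parenthesis | Individual OB provider |
| NEST Intervention item, control-arm sentence | Practice |
| Paragraph after that item | Branches designated for the intervention, so practice |
| Study Intervention description: "Those participants who are seeing a doctor or midwife randomized to the intervention arm may complete NEST online" | Either; a provider randomised by practice is also in an arm |
| Data Analysis | None |

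One statement stands alone against the rest, and it conflicts with its own item. The Data Analysis section does not decide between them.

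**Effect on the error term if practices were randomised**

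The documents give no sample size, alpha, number of practices, cluster size or intraclass correlation for the randomised comparison, so there is no plan figure to reproduce. Every input below is assumed: P = 3 or 5 providers per practice; m = 5 or 10 women per provider; practice ICC rc = 0.01, 0.02 or 0.05; additional provider ICC rp = 0.02 or 0.05; total variance 1; nominal two-sided alpha 0.05.

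- True variance of a practice mean: rc + rp/P + (1 − rc − rp)/(mP).
- Variance credited to it when providers are treated as independent: [rc + rp + (1 − rc − rp)/m]/P.
- Variance credited to it when women are treated as independent: 1/(mP).
- With R = true/credited, actual type I error = 2[1 − Φ(1.96/√R)].

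Provider as the unit:

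- Smallest case (P = 3, m = 5, rc = 0.01, rp = 0.05): true 0.01 + 0.0167 + 0.0627 = 0.0893; credited (0.06 + 0.188)/3 = 0.0827; R = 1.08; type I error 0.059.
- Largest case (P = 5, m = 10, rc = 0.05, rp = 0.02): true 0.05 + 0.004 + 0.0186 = 0.0726; credited (0.07 + 0.093)/5 = 0.0326; R = 2.23; type I error 0.189.

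Patient as the unit, which the analysis text does not rule out:

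- Smallest case (P = 3, m = 5, rc = 0.01, rp = 0.02): true 0.01 + 0.0067 + 0.0647 = 0.0813; credited 1/15 = 0.0667; R = 1.22; type I error 0.076.
- Largest case (P = 5, m = 10, rc = rp = 0.05): true 0.05 + 0.01 + 0.018 = 0.078; credited 1/50 = 0.02; R = 3.90; type I error 0.321.

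This is a large-sample approximation. Few practices per arm would make matters worse, because it ignores the small degrees of freedom.

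**Check by simulation, also on assumed inputs**

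The layout was 6 practices per arm, 4 providers per practice, 5 women per provider and provider ICC 0.05, with 20,000 null trials per setting. For practice ICC 0.02, 0.05 and 0.10, a t-test on provider means rejected in 7.6%, 11.3% and 16.7% of trials. A t-test on practice means rejected in 4.8% to 5.2%. In this layout the provider test has 48 − 2 = 46 degrees of freedom and the practice test 12 − 2 = 10. Analysing at the randomised level restores the nominal rate.

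**The case against.** The strongest reply is that the plan already answers the question. The randomisation paragraph is the only allocation procedure. It is explicit and rules out two arms in one clinic. The parenthesis allocates no one; it sits in an instruction about a questionnaire and may have meant only that patients are not individually randomised. The error-term problem comes mainly from the Data Analysis section, which omits clustering at every level, and correcting a parenthesis does not supply it. The calculations size an analysis on provider means that the plan never proposes.

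Most of this stands. It makes the practice the likely intended unit and limits how far the point can be pushed. A reader might infer more in four ways, and the documents support none of them:

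- **That clinics were mixed, or will be.** This would require staff to disregard the same-arm rule, and nothing shows that they did.
- **That the Study Intervention description is a second contradiction.** Its wording fits either unit.
- **That contamination dilutes the effect by some amount.** The documents give no basis for a figure. Contamination through mixed clinics would need providers to have been randomised individually, whereas the error-term calculation needs practices to have been randomised, so the two harms cannot be added together.
- **That providers work at two clinics or move between arms.** The recruitment text describes new staff, non-responders and providers who did not complete consent, not transfers.

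What does not stand is the conclusion that nothing need change. The parenthesis is in current text, in the item that selects who receives NEST. It conflicts with the allocation paragraph, and the section that should specify the analysis unit is silent.

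**Conclusion.** The contradiction is real and should be corrected before more providers are enrolled. It is most likely a wording slip rather than two competing designs.

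Its statistical importance depends on the analysis. If practices were randomised, using provider as the unit gives a type I error of about 6% to 19% for a nominal 5% test, and treating women as independent gives about 8% to 32%. These ranges are illustrations that rest wholly on the assumed cluster sizes and intraclass correlations above. They are not estimates for this trial. If providers were in fact randomised individually, these figures do not apply and the randomisation paragraph is the text that is wrong.

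**What to change.** 1. Confirm from the allocation record which unit was actually randomised.
2. If it was the practice, replace the parenthesis in the NEST Intervention item with: *(the unit of randomization is the outpatient practice; every participating provider, including one who joins later, takes the arm of that practice)*.
3. In that case, also state in Data Analysis that the NEST versus control comparison treats the practice as the randomised cluster, by a practice-level random effect or a cluster-level analysis, with small-sample degrees of freedom in either case.
4. If it was the provider, correct the randomisation paragraph instead, including its cluster definition, same-arm rule and contamination rationale, and carry that unit into Data Analysis.

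The Study Intervention description needs no edit, and no new rule restricting which providers may enrol patients is called for.

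The cost is a record check and wording in a few places. A practice-level analysis will give wider intervals than one that ignores practice, but that is the precision a practice-randomised design has.
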